1. INTRODUCTION

1.1. Background

In recent years, significant progress has been made in cancer treatment, and small molecular targeted therapies inhibiting internal driving factors of tumor angiogenesis and cancer cell growth, as well as immunotherapies enhancing anti-cancer immunity of the patients, have been approved by regulatory agencies in many countries. With the deepening of the understanding of the body's immune system and the rapid development of biotechnology, the immunotherapy has become an important means of cancer treatment, and it is occupying an increasingly important position in the comprehensive treatment system of tumors.

Targeted therapy may result in significant clinical response for numerous types of tumors. However, the duration of response is short, and the initial responses are usually accompanied by tumor immune escape and clinical recurrence within a few months. In comparison, immunotherapy is also applicable to many types of cancers, and can provide a longer duration of response in some patients. Contrary to standard chemotherapy or targeted therapy which directly acts on the cancer cells, immunotherapy not only kills cancer cells directly, but more importantly, also enhances the immune response of the body by acting on the immune system and ultimately prolonging the survival of patient.

Programmed cell death protein 1, or PD-1, is a negative costimulatory molecule discovered in recent years. PD-1's ligands include PD-L1 and PD-L2, which can bind specifically to PD-1. Through high expression of PD-L1, cancer cells bind to the PD-1 molecules on T lymphocytes, which transmit a negative regulatory signal, resulting in the induction of apoptosis and immune incompetence of tumor antigen-specific T cells, allowing the cancer cells to evade immune monitoring and killing. PD-1 inhibitors are new immunotherapeutic drugs of interest. By blocking the PD-1/PD-L1 signaling pathway, the anti-tumor activity of T lymphocytes is up-regulated, resulting in apoptosis of the cancer cells.

Since 2014, the U.S. Food and Drug Administration (FDA) has approved anti-PD-1 monoclonal antibodies, nivolumab from BMS and pembrolizumab from Merck for the treatment of patients with advanced melanoma, non-small cell lung cancer, renal cell carcinoma, head and neck cancer, Hodgkin's lymphoma, as well as HCC previously treated with sorafenib, including those with advanced disease, refractory to standard treatment, or without effective treatment options. They are also used as first or second line treatment currently. In addition, due to its long-lasting efficacy and relatively mild adverse reactions, anti-PD-1 monoclonal antibodies have been studied in hundreds of clinical trials internationally for advanced solid tumors and malignant hematologic diseases, including monotherapy and combination therapy. Results have all shown better efficacy and longer survival compared to existing treatments.

On 23 Sept., 2017, the FDA approved nivolumab for the treatment of patients with HCC previously treated with sorafenib based on data from trial Checkmate-040, marking the beginning of the era of immunotherapy for HCC. This was a single-arm, dose-escalation and dose-expansion Phase I/II clinical trial in advanced HCC: a total of 262 subjects (48 in the dose-escalation stage and 214 in the dose-expansion stage) with or without chronic hepatitis were enrolled to evaluate the efficacy and safety of nivolumab.

In the dose-escalation stage, subjects received nivolumab 0.1-10 mg/kg one every 2 weeks.

In the dose-expansion stage, subjects received nivolumab 3 mg/kg once every 2 weeks.

The primary endpoints were safety and tolerability for the dose-escalation stage and ORR for the dose-expansion stage. Results showed that the nivolumab is safe and well-tolerated. The ORR was 15% in the dose-escalation stage and 20% in the dose-expansion stage. Most importantly, results showed that nivolumab is also effective in patients with Hepatitis B.

Subjects who had not received sorafenib had a 12-month survival of 73% using nivolumab as first-line treatment. Subjects previously treated with sorafenib had a 12-month survival of 58-60% with nivolumab.

Despite the unprecedented success of such therapies, it should not be overlooked that a considerable proportion of patients still do not respond to the therapy. From the current point of view, the combination therapy will be one of the inevitable trends in the future development of immunotherapy of tumors. How to carry out the combination therapy is a problem to be solved by the medical community.

There are currently a large number of Phase I/II clinical trials that combine targeted therapy with immunotherapy. The rationale supporting these combination therapies is that the combination of the two therapies combines different immunological and tumor biological mechanisms that enhance the anti-cancer activity; In addition, some evidence suggests that targeted therapies can enhance certain aspects of the "cancer-immune cycle" (such as tumor antigenicity, T cell initiation/transport/infiltration, etc.) to synergistically enhance the efficacy of the immunotherapy. In particular, targeted therapies targeting the mitogen-activated protein kinase (MAPK) and the vascular endothelial growth factor (VEGF) pathways, including drugs such as sunitinib, can have a direct impact on tumor cell growth and tumor angiogenesis, as well as on tumor antigenicity and intratumoral T cell infiltration. Their impact on the patient's immune response is beyond their role in tumor biology, providing a strong basis for the combination therapy.

Current combination therapies have largely focused on advanced melanoma, lung cancer, and renal cell carcinoma. Good clinical prospect is also seen in the treatment of liver cancer, ovarian cancer, colorectal cancer, head and neck cancer, and Hodgkin's lymphoma. Some key factors should be considered in the clinical development of combination therapies, such as optimizing dosing regimens, minimizing treatment-related toxicity, selecting appropriate endpoints to assess the efficacy, and so on.

This clinical trial involves recombinant humanized anti-PD-1 monoclonal antibody injection (SHR-1210), a new class 1 therapeutic biological product developed by Jiangsu Hengrui Pharmaceuticals Co., Ltd. that has not been marketed both in China and abroad. Preclinical trial data show that SHR-1210 has comparable *in vivo* efficacy and safety with those of similar drugs abroad. Since 2015, Jiangsu Hengrui Pharmaceuticals Co., Ltd. conducted Phase I/II clinical trials of several types of tumors in both Australia and China, and preliminarily validated the safety, tolerability and efficacy of SHR-1210 monotherapy in the treatment of advanced solid tumors. For details regarding SHR-1210, please refer to the SHR-1210 Investigator's Brochure provided by the sponsor.

This study also involves apatinib mesylate (trade name: Aitan), which was launched in 2014 by Jiangsu Hengrui Pharmaceuticals Co., Ltd. Apatinib is a small molecule targeted medicine that is a vascular endothelial growth factor receptor (VEGFR) tyrosine kinase inhibitor. Apatinib exerts its anti-angiogenic effect mainly by inhibiting VEGFR. Preclinical studies have shown that it's superior to similar product in anti-tumor effect. In 2014, apatinib was approved for patients with refractory or relapsed advanced gastric adenocarcinoma or gastroesophageal junction adenocarcinoma who have previously been treated with at least 2 systemic chemotherapies.

The recommended dosage of apatinib mesylate in patients with refractory or relapsed advanced gastric adenocarcinoma or gastroesophageal junction adenocarcinoma previously treated with at least 2 systemic chemotherapies is 850 mg orally (p.o.) once daily (q.d.). The treatment is in cycles of 28 days (not including treatment interruption), and is continuously given until disease progression or unacceptable toxicity. Treatment can be interrupted (no more than 2 weeks) or the dose can be adjusted to 750 or 500 mg in case of Grade 3/4 hematologic or non-hematologic toxicities.

Primary hepatocellular carcinoma (HCC) is a typical hypervascular tumor. Its occurrence, development, metastasis, and invasion are all closely related to angiogenesis. A randomized, open-label, multi-center, Phase II clinical trial evaluating apatinib mesylate in advanced hepatocellular carcinoma was conducted from 2010 to 2013, led by the 81th Hospital of the Chinese People's Liberation Army. A total of 121 subjects received the medication. In the full analysis set, the median time to progression (mTTP) was 4.21 months and median overall survival (mOS) was 9.71 months in the 850 mg group. The mTTP was 3.32 months and mOS was 9.82 months in the 750 mg group. There were no statistically significant differences in mTTP and mOS between the 850 mg and 750 mg groups. The incidence of adverse reactions was 95.71% in the 850 mg group and 90.20% in the 750 mg group. The incidence of severe adverse reactions was 58.57% and 58.82%, respectively. The difference was not statistically significant. Therefore, 750 mg was the recommended dose for Phase III clinical trials due to its superior tolerability. The recommended dosing regimen is 750 mg, p.o., q.d., continuous administration in

cycles of 28 days (not including treatment interruption), until disease progression or unacceptable toxicity. Treatment can be interrupted (no more than 2 weeks) or the dose can be adjusted to 500 or 250 mg in case of Grade 3/4 hematologic or non-hematologic toxicities.

A randomized (2:1), open-label, placebo-controlled, multi-center, Phase III clinical trial evaluating the efficacy and safety of apatinib as second-line treatment of advanced HCC is currently underway. Patients with advanced HCC who failed sorafenib or systemic chemotherapy or patients with relapse or unacceptable toxicity were recruited. As of December 2017, a total of 400 subjects were enrolled. Adverse events that have been observed include proteinuria, elevated blood pressure, thrombocytopenia, hand-and-foot syndrome, and elevated total bilirubin. For details regarding apatinib mesylate, please refer to the prescribing information for apatinib mesylate and the Investigator's Brochure provided by the sponsor.

Based on data from large-scale randomized, controlled trials described above, the maximum tolerated dose for apatinib mesylate monotherapy is 850 mg, q.d., and the minimum effective dose is 250 mg, q.d. Main adverse reactions include hand and foot skin reactions, hypertension, elevated transaminase, elevated bilirubin, decreased WBC, thrombocytopenia, diarrhea, esophagitis, nausea, and asthenia. Most were mild to moderate reactions. Since toxicity and efficacy may be compounded with combination therapy, 250 mg q.d. is selected as the dose for combination therapy. The dosing frequency for apatinib may be adjusted subsequently based on subject's tolerability and adverse reactions.

This study explores a new combination therapy, which is urgently needed in clinical practice, not only for laying a foundation for future studies, but also for exploring biomarkers related to cancer immunity. Therefore, it has important scientific significance and clinical value.

1.2. Scientific Basis

Primary liver cancer is a common cancer in China. It currently ranks the 4th among common malignant tumors and the 3rd among causes of cancer deaths, and heavily threatens the lives and health of Chinese people. Primary liver cancer mainly includes hepatocellular carcinoma (HCC), intrahepatic cholangiocarcinoma (ICC), and a mixed HCC-ICC type. These three types differ a great deal in pathogenesis, biological behavior, histological morphology, treatments, and prognosis. HCC accounts for more than 85-90% of all liver cancers.

Treatment regimens for advanced HCC is very limited. Sorafenib is the only first-line medicine approved by the FDA and NMPA for the treatment of advanced HCC. When compared to placebo, sorafenib can effectively prolong the time to progression and overall survival in patients with advanced HCC. However, the overall treatment efficacy of sorafenib against HCC is unsatisfactory. Many studies have shown that the objective response rate (ORR) is < 10% and mOS is < 10 months when sorafenib is used as first-line treatment for advanced liver cancer. An effective treatment for advanced HCC is urgently needed.

1.2.1. Rationale

An earlier study involving SHR-1210 in combination with apatinib in advanced HCC (results yet to be published) found that a fixed dose of SHR-1210 200 mg plus apatinib 250 mg orally q.d. was a tolerated dose. As of 25 Dec., 2017, a total of 14 patients with advanced HCC were enrolled to receive a fixed dose of SHR-1210 200 mg plus apatinib 125 mg or 250 mg, p.o., q.d. In the 4 subjects receiving SHR-1210 200 mg plus apatinib 125 mg, 2 had an increased dose of apatinib to 250 mg q.d. during the treatment period. The other 10 subjects received SHR-1210 200 mg plus apatinib 250 mg.

All subjects were HBV-positive, and 11 of the 14 subjects had previously failed sorafenib. A total of 13 subjects completed at least 1 efficacy evaluation after enrollment. There were 7 cases of partial response (PR) and 5 cases of stable disease (SD). The 6-week disease control rate was over 90%. Most subjects continued to benefit from the treatment, and the median duration of treatment was more than 7 months.

Other than the efficacy in advanced HCC, the tolerability and preliminary efficacy of SHR-1210 plus apatinib in non-squamous and squamous cell lung cancer were also explored. Initial results showed that SHR-1210 plus apatinib is also safe and well-tolerated in patients with lung cancer, and the combination therapy is superior to anti-PD-1 antibody monotherapy.

Multiple studies have demonstrated the safety, tolerability, and preliminary efficacy of SHR-1210 plus apatinib, suggesting that the combination therapy is superior to anti-PD-1 antibody monotherapy.

1.2.2. Basis for development

Sorafenib is the first-line treatment for advanced HCC. Sorafenib achieved an ORR of 3.3-8.3%, a TTP of 2.8-3.6 months, and an OS of ~10 months when used as first-line monotherapy for advanced HCC in the Asians, with limited efficacy.

There is yet a widely accepted standard for treating HCC in patients who failed sorafenib. Anti-PD-1 antibodies demonstrated significant preliminary efficacy against HCC in patients who failed sorafenib. Nivolumab achieved an ORR of 14% when used as second-line treatment for HCC in the Caucasian population. Regorafenib achieved an ORR of 11% in patients with advanced HCC who had disease progression despite sorafenib treatment (excluding those intolerant of sorafenib). However, these clinical trials mostly enrolled Caucasians, most of which were HCV-positive. Stratified analysis of data from previous studies showed that HBV infection is a poorer prognostic factor than HCV infection, and ~90% of all Chinese patients with liver cancer are HBV-positive.

An effective treatment for Chinese patients with HCC is urgently needed. The tolerability and safety of SHR-1210 plus apatinib have been adequately studied. Its preliminary efficacy in HCC patients refractory to sorafenib is significant. Further exploration of this treatment against advanced HCC is well supported.

1.2.3. Rationale of regimen

Numerous studies in various cancers such as non-squamous and non-small cell lung cancer, HCC, ICC, and gastric adenocarcinoma have demonstrated that: A fixed-dose of SHR-1210 200 mg plus apatinib 250 mg p.o., q.d., is a tolerated dose. Apatinib 250 mg is superior to 125 mg in terms of efficacy when combined with SHR-1210. Apatinib 250 mg is better tolerated than 375 mg when combined with SHR-1210. In a Phase II study involving SHR-1210 plus apatinib in non-squamous, non-small cell lung cancer, SHR-1210 plus apatinib 375 mg resulted in experiencing Grade 3 rash in multiple subjects and treatment interruption due to adverse events in multiple subjects during the tolerability observation. In a Phase II study involving SHR-1210 plus apatinib in advanced primary liver cancer (patients with HCC and ICC were enrolled), multiple subjects experienced Grade 3 thrombocytopenia after receiving SHR-1210 plus apatinib 375 mg.

Therefore, a fixed dose of SHR-1210 200 mg q2w plus apatinib 250 mg p.o., q.d., is selected for this study. The efficacy and safety of this combination are studied in patients with advanced HCC refractory to sorafenib or patients unwilling or unable to afford sorafenib.

1.3. Potential Risks and Benefits

1.3.1. Known potential risks

Any study drug or treatment may have unpredictable or even serious side effects.

As of 25 Aug., 2017, among all subjects who have received SHR-1210, 214 (34.3%) reported skin toxicity event hemangioma (which has not been reported for other anti-PD-1 IgG4 antibodies). Among subjects who experienced hemangioma, 6 underwent surgery and/or were hospitalized for long-term clinical observation. Therefore, hemangioma in these subjects were considered as SAEs. All hemangiomas were reported as Grade ≤ 2 . The hemangiomas resolved after discontinuation of SHR-1210.

In SHR-1210 studies conducted in Australia and China, 7 (1.1%) subjects reported pneumonitis SAEs and 3 (0.5%) reported interstitial lung disease SAEs.

Other immune-related AEs frequently reported for other anti-PD-1 antibodies are considered to be class effects and are also observed in SHR-1210 clinical studies. These included AST elevation (73 subjects, 11.7%), ALT elevation (58 subjects, 9.3%), rash (57 subjects, 9.1%; preferred terms include rash, rash macular, rash maculo-papular, rash erythematous, rash pustular,

and rash pruritic), diarrhea (44 subjects, 7.1%), hypothyroidism (37 subjects, 5.9%), and hyperthyroidism (8 subjects, 1.3%). These events are considered to be related to the investigational drug due to their high incidence and consistency with safety outcomes of other anti-PD-1 antibodies. Note that only 1 case of diarrhea was reported as an SAE. There was no colitis reported as an SAE. Therefore, many diarrhea events may not be immune-related, but may be caused by underlying conditions. In addition, many patients with AST and ALT elevations were with liver cancer. Among the 659 subjects enrolled in SHR-1210 studies in China, nearly a quarter were patients with primary liver cancer.

Analyses showed that the investigator-assessed immune-mediated adverse events assessed where SHR-1210 could not be ruled out as a potential cause were prominently skin toxicities (such as rash or hemangioma of skin). Most immune-related adverse events were Grades I-II.

The above data was compared with adverse reactions reported for other approved anti-PD-1 antibodies - nivolumab from BMS and pembrolizumab from Merck. The incidence and severity were both lower. Overall, the adverse reactions are expected to be similar to those of nivolumab and pembrolizumab.

Recommended management of common side effects and protocol-specified dose modifications have been established for this study, so that subjects may continue to receive SHR-1210 treatment, given that subjects will benefit clinically.

Overall, anti-PD-1 antibodies as monotherapy are superior to traditional chemotherapy and targeted therapy in terms of adverse reactions. When compared to chemotherapy, the combination treatment demonstrated an increase in incidence of fatigue, nausea, rash, and alopecia, but is well tolerated. Immune-related adverse reactions still require special interest, including immune-related interstitial lung disease, rash, thyroiditis, as well as those with lower incidence ($\leq 1\%$) such as vitiligo, colitis, nephritis, hepatitis, uveitis, adrenal insufficiency, and nerve palsy. These immune-related adverse reactions were mostly mild and manageable. Very few were SAEs or potentially life-threatening. By established procedures for toxicity management, the majority of immune-mediated adverse events can be adequately controlled.

Subjects receiving macromolecular protein monoclonal antibody drugs may also encounter other risks including infusion reactions, which prominently manifest as chills, rigors, facial and peripheral cyanosis, followed by fever and probably accompanied by nausea, vomiting, headache, dizziness, dysphoria, delirium, etc. In severe cases, there may be coma, fall of blood pressure, and symptoms such as shock and respiratory failure etc. These risks may arise due to various factors during intravenous infusion, such as pyrogens, drugs, impurities, low temperature of injection, high concentration of drug, and high rate of infusion, etc. SHR-1210 is a fully humanized monoclonal antibody. Its reported infusion reactions were low in incidence and mild in severity.

A tumor biopsy may be required for subjects in this study in order to obtain tumor tissues (after obtaining informed consent). This is required for determining PD-L1 expression level and other biomarkers for predicting treatment response, and can generally be completed successfully. However, due to health status of subjects, individual differences, and certain unpredictable factors, anaphylactic shock due to anesthesia, local pain, local infection, local bleeding, and local nerve injury may occur, or severe occult diseases may be induced. Also, pathological examinations for malignant tumors may not be completed with the tissue obtained from one biopsy. Thus, biopsies may be repeated when necessary.

Medical examinations performed during the course of the study may also bring potential risks to the subjects. Frequent imaging tumor assessments may expose subjects to low-dose radiation more frequently. However, since advanced or metastatic non-small cell lung cancer usually progresses rapidly, frequent imaging tumor assessments are necessary to determine whether the subject has disease progression.

1.3.2. Known potential benefits

In summary, existing treatments pose limited efficacy against advanced HCC. Less than 10% of all patients achieve response from first-line treatment with sorafenib. Also, a large number of patients are unable to afford the medication due to the high spending on sorafenib. Preliminary clinical results of nivolumab and SHR-1210 in advanced liver cancer showed that anti-PD-1 is effective in advanced liver cancer. The ORR of anti-PD-1 antibodies in patients with advanced HCC who failed sorafenib reached approximately 14%, which is superior to current treatments. SHR-1210 plus apatinib also achieved favorable preliminary results in the treatment of advanced HCC. Participating in this study and receiving study treatment may bring about clinical benefits for patients with advanced HCC, providing an effective treatment option for these patients.

2. OBJECTIVES AND ENDPOINTS

2.1. Study Objectives

2.1.1. Primary objective

- To evaluate objective response rate (ORR) of SHR-1210 in combination with apatinib mesylate in patients with advanced hepatocellular carcinoma

2.1.2. Secondary objectives

- To observe and evaluate the progression-free survival (PFS), duration of response (DOR), time to response (TTR), disease control rate (DCR), overall survival (OS), and 9-month/12-month survival rates of SHR-1210 in combination with apatinib mesylate in patients with advanced hepatocellular carcinoma;

- To determine the safety of SHR-1210 in combination with apatinib mesylate in patients with advanced hepatocellular carcinoma.

2.1.3. Exploratory objectives

- To explore the anti-HBV effects of SHR-1210 in combination with apatinib;
- To explore the biomarkers for predicting response;

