2.2.3. Exploratory endpoints

- Serum HBV DNA levels and the rate of HBsAg loss;
- The relationship between response and PD-L1 expression levels, the proportion of positive cells, and/or other biomarkers such as baseline tumor mutational burden (TMB);

- The relationship between baseline alpha fetoprotein level and response;
- The relationship between response and baseline levels of acyl-CoA: sterol O-acyltransferase 1 (SOAT1), Niemann–Pick C1 protein (NPC1), and transforming growth factor beta (TGF- β);

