3.2. Reducing Bias

3.2.1. Enrollment/randomization/blinding

This is a single-arm study. Subjects are allocated sequentially. There are no randomization and blinding process.

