11. Clinically significant bleeding symptoms or clear bleeding tendency within 3 months prior to enrollment, such as coughing > 2.5 mL of blood daily, gastrointestinal bleeding, esophageal varices with bleeding risks, hemorrhagic gastric ulcer, or vasculitis. In case of positive fecal occult blood at baseline, a re-examination is needed, and a gastroscopy is required if it is still positive. The subject will be excluded if the gastroscopy indicates severe esophageal varices (except for those where such conditions have been ruled out by gastroscopy within 3 months prior to enrollment);
12. Events of arterial/venous thrombosis within 6 months prior to enrollment, such as cerebrovascular accidents (including transient ischemic attacks, cerebral hemorrhage, cerebral infarction), deep vein thrombosis, and pulmonary embolism;
13. Known hereditary or acquired hemorrhage and thrombophilia (such as hemophilia, coagulopathy, thrombocytopenia, etc.);
14. The routine urinalysis indicates that urine protein is $\geq ++$ and confirms that 24h urine protein is ≥ 1.0 g;
15. Patients who have previously received radiotherapy, chemotherapy, hormone therapy or surgery that is less than 4 weeks before the study after the end of such treatments (last dose); molecular targeted therapy (including oral targeted drugs in other clinical trials) is less than 5 drug half-lives from the first dose; or patients with adverse events caused by previous treatment (except for alopecia) that have not returned to \leq CTCAE grade 1;
16. Patients with active infection, fever ≥ 38.5 °C of unknown causes within 7 days prior to administration, or WBC count $> 15 \times 10^9/L$ at baseline;
17. Patients with congenital or acquired immunodeficiency (such as HIV positive);
18. HBV DNA > 2000 IU/mL (or 10^4 copies/mL); or HCV RNA $> 10^3$ copies/mL; or HBsAg+ and anti-HCV antibody positive;

19. Patients with other malignancies currently or within the past 3 years (except for cured basal cell carcinoma and cervical carcinoma in situ);
20. Patients with bone metastasis who have received a palliative radiotherapy in an area of > 5% of bone marrow area within 4 weeks prior to the participation in this study;
21. Patients who have previously received other anti-PD-1 antibody therapies or other immunotherapies targeting PD-1/PD-L1, or have previously received apatinib treatments;

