5.5. Concomitant Therapies

Concomitant therapies refer to any other treatments that are given for the interest of subjects as determined by the investigator.

All concomitant medications and treatments within 30 days prior to the start of study treatment and during the study must be documented in the eCRF in strict accordance with the GCP.

Once a subject discontinues the investigational treatment, only concomitant medication or treatment for new or unresolved treatment-related adverse events are recorded, until at least 30 days after the last dose.

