5.5.2. Supportive care

Palliative and supportive care for disease-related symptoms will be based on the investigator's judgment and relevant guidelines. The best oral anti-viral drug for the treatment of hepatitis B is permitted during the study, but interferon is prohibited.

Subjects should be given optimal supportive care during the treatment. Comorbidities and various adverse reactions, especially immune-related adverse reactions, should be actively treated.

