The window period for imaging examination schedule is ± 7 days. Unscheduled imaging examinations can be performed when progressive disease is suspected (such as worsening of symptoms).

[Thyroid function test] On D1 \pm 7 d of Cycle 2, then on D1 \pm 7 d of every 3rd cycles subsequently;

[Alpha-fetoprotein] On D1 \pm 7 d every 2nd cycle;

[HBV DNA and HBsAg quantitative tests] Perform on D1 \pm 7 d of every 2nd cycle during the study for those with abnormal HBsAg at baseline;

[Blood pressure monitoring] During the treatment period, blood pressure is monitored by the subject and documented in the patient's daily log. Blood pressure should be measured at least 3 times per week during the first 2 cycles. For subjects with abnormal blood pressure, the blood pressure should be measured daily; otherwise, the blood pressure should be measured at least 2 times per week after Cycle 2. The investigator or study nurse will also measure the blood pressure at each visit;

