### **5.4.5. Other analyses**

Based on FAS, the best post-baseline changes in the sum of target lesion diameter values from baseline over time is plotted (i.e. waterfall plot, which is grouped by the best overall response).

Based on FAS, the swimmer plots of objective response and disease control are drawn. A swimmer plot of treatment and survival status of subjects who continue treatment after PD is drawn.

Based on FAS, the consistency of imaging PD events in each group is analyzed according to the consistency analysis of IRC and investigator assessment (LE) among different populations. Similar analyses are carried out for CR/PR consistency and BOR consistency of imaging assessment in each group.

Based on FAS, the change of target lesions of subjects with best overall response of CR/PR/SD (assessed by IRC based on RECIST v1.1) from baseline over time is plotted (i.e., spider plot).

Based on FAS, the change of target lesions of subjects who continue study drug therapy after PD (assessed by investigators based on RECIST v1.1) from baseline against time is plotted (i.e., spider plot).

Based on FAS, HBsAg loss is defined as the number and percentage of subjects who have positive baseline value and any negative post-baseline test values.

Based on FAS, the overall survival curve is plotted according to different populations and grouped by CR + PR, SD, and PD according to best overall response (best overall response is assessed by IRC based on RECIST v1.1, excluding subjects with the best overall response of NE).

The information of subsequent post-withdrawal anti-cancer therapy (including chemotherapy, radiotherapy, target therapy, surgery, interventional procedure, traditional Chinese medicine, and other categories) used after treatment discontinuation is summarized to analyze whether the anti-cancer therapy used after treatment discontinuation in each population is balanced, and listed. In addition, the duration (month) of a particular category of subsequent post-withdrawal anti-cancer therapy (chemotherapy, target therapy, and immunotherapy) after treatment discontinuation is summarized by using descriptive statistics such as number of subjects (n), mean, standard deviation, median, quartile (Q1 and Q3), minimum (min), and maximum (max).

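### The planned HBV output cannot show an anti-HBV effect of the combination: one arm, oral HBV antivirals permitted, and no HBV result separated by antiviral use

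*Protocol*

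**What the plan says.** **Objective and endpoints.** Protocol 2.1.3 gives the objective as "To explore the anti-HBV effects of SHR-1210 in combination with apatinib". Protocol 3.1 and SAP 2.1 describe it as the anti-HBV efficacy of the combination. The endpoints in Protocol 2.2.3 are "Serum HBV DNA levels and the rate of HBsAg loss".

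**Design.** Protocol 3.2.1: "This is a single-arm study. Subjects are allocated sequentially". There is no comparator.

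**Entry and permitted treatment.** Protocol 4.2, item 18, excludes patients with "HBV DNA > 2000 IU/mL (or 10^4 copies/mL"). Protocol 5.5.2 states: "The best oral anti-viral drug for the treatment of hepatitis B is permitted during the study, but interferon is prohibited". It sets no condition on when the antiviral was started or whether its use is unchanged.

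**Measurement.** Under Protocol 6.2, HBV DNA and HBsAg are quantified "every 2nd cycle during the study for those with abnormal HBsAg at baseline".

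**Analysis.** Protocol 11.5.5 summarizes HBsAg levels descriptively and does not mention HBV DNA. SAP 4.3.5 names HBsAg loss only. SAP 5.4.5, on the full analysis set, says "HBsAg loss is defined as the number and percentage of subjects who have positive baseline value and any negative post-baseline test values". SAP 5.5.3 lists virology results without summarizing them. The subgroups in SAP 5.4.4 apply to ORR, PFS and OS; HBV infection is one of them, antiviral use is not.

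**Medication data.** Protocol 5.5: "All concomitant medications and treatments within 30 days prior to the start of study treatment and during the study must be documented". SAP 5.2.6 lists these records and summarizes them by ATC1 and verbatim term, with no link to HBV outcome.

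**The concern.** The objective names the study drugs as the agent. A permitted antiviral acts on the same virus, in the same patients, over the same period. With one arm and pooled reporting, a lost HBsAg in a patient taking an antiviral counts the same as one in a patient taking none.

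The stake is an unsupported statement about anti-HBV activity. It could travel beyond this report: Protocol 7.3 lists HBV DNA and HBsAg loss among the biomarkers to be evaluated, and says that exploratory biomarker results may be combined with other studies to form hypotheses for later validation.

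**Working it through.** Neither document gives a sample size, precision target or assumed rate for the HBV objective, so there is no plan figure to reproduce. The check is mainly one of logic, with two illustrations.

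**1. What the pooled rate identifies.** Among subjects HBsAg-positive at baseline, let w be the share on an antiviral, and let p_U and p_N be the HBsAg-loss rates in users and non-users. The planned figure is

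p = w·p_U + (1 − w)·p_N.

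The plan reports p alone. It does not report p_U or p_N, and it does not tabulate w in this population. Reporting them would still leave p_U a mixture of antiviral, study drugs and background loss, and p_N a mixture of study drugs and background loss, because there is no control arm. So the pooled p cannot be read as an effect of the combination, and separating users from non-users removes only part of the ambiguity.

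**2. What the plan does with each endpoint.**

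| Endpoint (Protocol 2.2.3) | Planned HBV output | Split by antiviral use |
|---|---|---|
| HBsAg loss | One count and percentage on the full analysis set (SAP 5.4.5) | No |
| HBV DNA | Listing only (SAP 5.5.3); not named in Protocol 11.5.5 | No |

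**3. What the entry ceiling does.** log10(2000) = 3.30. The assay limit is not given. Assuming a quantification limit L between 10 and 100 IU/mL, the largest observable fall is 3.30 − log10(L):

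- L = 10: 3.30 − 1 = 2.30 log10.
- L = 100: 3.30 − 2 = 1.30 log10.

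A subject already below the limit at baseline can show no fall. This bears on HBV DNA. The ceiling places no direct restriction on HBsAg loss.

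**4. How informative a no-antiviral group could be.** Inputs:

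- Enrolment of 136, or 120 + 56 = 176 if the sorafenib-refractory group is expanded (Protocol 3.1).
- About 90% HBV-positive. This is the background figure for Chinese liver-cancer patients in Protocol 1.2.2, not an expected count for this trial.
- An assumed 5% to 40% taking no antiviral. The documents give no rate.

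HBV-positive: 0.9 × 136 = 122.4, about 122; 0.9 × 176 = 158.4, about 158. With zero losses among k non-users, the Clopper-Pearson upper 95% limit is 1 − 0.025^(1/k).

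| Enrolled | Share without antiviral | k | Upper limit for 0 of k |
|---|---|---|---|
| 136 | 5% | 6 | 46% |
| 136 | 40% | 49 | 7% |
| 176 | 5% | 8 | 37% |
| 176 | 40% | 63 | 6% |

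For k = 20 the limit is 1 − 0.025^(1/20) = 16.8%. The separated result could be reasonably tight or nearly empty, and the documents do not say which.

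**The case against.** The strongest defence is that this is one exploratory, descriptive output. No hypothesis or decision rule uses HBV data; the rules in Protocol 11.2 and SAP 3 concern ORR. SAP 4.3.5 words the endpoint neutrally, as HBsAg loss during the trial. Medications and virology are both listed, so a reader could check antiviral use against each HBsAg loss by hand. Inability to isolate a drug effect follows largely from having no control arm, and no tabulation changes that. Non-users are self-selected and may be few.

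Most of this stands, and it limits the point. It does not remove it. The objective and the design sections still speak of an effect or efficacy of the combination, and the only planned HBV rate is the one least able to support that. A manual cross-check of listings is not a planned analysis.

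The defence is also right about the data. Protocol 5.5 requires concomitant medication to be documented but names no start or change dates, and the SAP 5.1.6 imputation rules do not cover such dates. A reader might infer that antiviral start dates are in the eCRF and the bias is therefore fully avoidable; the documents do not establish either.

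**Conclusion.** The point holds within limits. The planned HBV output cannot separate SHR-1210 plus apatinib from a permitted antiviral. HBV DNA, one of the two named HBV endpoints, has no planned summary in the SAP, and its observable fall is capped by the entry criterion. This rests on the text alone. The size of any bias is unknown, because no antiviral-use rate is given; the figures in steps 3 and 4 depend on the assumptions stated there. The primary ORR analysis is untouched.

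Stronger readings that a reader might infer, and why they fail:

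- **That the plan credits viral control to the study drugs.** Neither document states an attribution. The risk lies in the objective's wording combined with a pooled figure.
- **That a given share of patients will falsely appear to clear HBV DNA.** No HBV DNA clearance rate is planned, so such a figure would describe an output that does not exist.
- **That the entry ceiling undermines HBsAg loss.** It restricts HBV DNA only.
- **That HBsAg loss is counted over everyone.** SAP 5.4.5 counts subjects positive at baseline; at most, the denominator on the full analysis set is unclear.
- **That results in non-users would show an anti-HBV effect.** That group has no control and is not a random subset.

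**What to change.** In SAP 5.4.5 and Protocol 11.5.5:

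1. Derive antiviral status from recorded concomitant medication: none; in use and unchanged since before baseline; started or changed shortly before first dose or on study. Apply the last two categories as far as recorded dates allow, with an unclassifiable category where they do not. The ATC1 summary does not itself identify HBV antivirals, so define them from a reviewed list of verbatim terms.
2. Report HBsAg loss by this status, with subjects HBsAg-positive at baseline as the stated denominator.
3. Report HBV DNA change by this status among subjects with detectable HBV DNA at baseline. This also supplies the missing summary for a named endpoint.
4. Label the pooled figure *HBV status under study treatment and permitted antivirals*, and make no statement of an anti-HBV effect of the combination from it. Keep the separated results descriptive as well.

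The cost is SAP and protocol wording, one derived variable and one table, using medication and virology data already recorded. It adds no visit or sample and leaves the rules on antiviral use as they are. The downside is that the no-antiviral group may be too small to inform, and the split reduces the confounding without removing it.
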